### **5.1.1.4 Protocol deviations**

Important protocol deviations (IPDs) are identified as part of the data cleaning process in the Data Cleaning Plan (DCP). The objective of the data cleaning meeting will be to review and update (if necessary) the important protocol deviations in the DCP and discuss exclusion of study participants from analysis populations.

Furthermore, overall trends in protocol deviations will be discussed at the Data Evaluation Meetings (DEM). Through this data cleaning and evaluation process, all decisions regarding important protocol deviations and exclusions from analysis populations will be made. Protocol deviations (eg, missing assessments or visits) related to COVID-19 will be listed separately.

Accepted deviations from theoretical time points will be described in the appropriate documents and included in the trial master file (TMF).

After resolution of all issues, and documentation of all decisions, the database will be locked.

#### **5.1.1.4.1 COVID-19 related protocol deviation**

UCB guidance on deviations and amendments related to SARS-CoV2 pandemic states that the identified COVID-19 related PDs need to be reviewed on an ongoing basis in case they collectively or individually may give reason to consider a protocol amendment (for example study design changes or changes to primary analysis methods etc). To facilitate this ongoing review, IPDs will be categorized as related to COVID-19 within the Clinical Trial Management System (CTMS). The COVID-19 related IPDs will be listed separately for consideration at the DEM.

### **5.1.1.5 Treatment assignment and treatment groups**

Treatment assignment for the SS and PKS will be according to the actual treatment received.

Listings and summaries will be presented by treatment group and overall where applicable. The following order will be used in the TFLs:

- Bimekizumab-AI-2mL: Single dose sc injection, bimekizumab 1x320mg, device presentation 2mL AI
- Bimekizumab-AI-2x1mL: Single dose sc injection, bimekizumab 2x160mg, device presentation 1mL AI
- All study participants

For analysis conducted using the all study participants set, an additional group for participants not randomized may be displayed, as applicable.

#### **5.1.1.6 Coding dictionaries**

All AEs and medical history will be coded for analysis according to the Medical Dictionary for Regulatory Activities (MedDRA® 19.0) coding dictionary. Prior and concomitant medications will be coded for analysis using the World Health Organization Drug dictionary (WHO-DD Mar 2021). Medical procedures will not be coded.

#### **5.1.1.7 Multicenter studies**

This is a multicenter study with participation of at a maximum of 2 sites. In general, the data from both sites will be pooled for the purpose of the analysis. However, the effect of center on results will be evaluated in sensitivity analysis as mentioned in Section 5.4.2.3.

### **5.2 Participant Dispositions**

Participant screening and primary reason for screen failure will be summarized using the All Study Participants Set. The summary will include the following:

- Number of participants screened
- Number and proportion of participants with screen failures (Not counting successfully rescreened participants)
- Number and proportion of screen failures by primary reason for screen failure (based on the later screening visit, in case of rescreen).

Additionally, the reasons for screen failures will be summarized by during and post the COVID-19 pandemic based on the screen failure date relative to the pandemic cut-off date.

Disposition of analysis sets will be summarized using the All Study Participants Set. The summary will include the total number of participants in the All Study Participants Set, as well as the number and percentage of participants in each analysis set by treatment group. The percentages will be calculated based on the RS.

Study completion/discontinuation and primary reason for discontinuation will be summarized by treatment group and overall using the RS. The summary will include the following:

- Number and percentage of participants that started the study
- Number and percentage of participants completing the study
- Number and percentage of participants discontinuing the study
- Number and percentage of participants discontinuing the study by primary reason for discontinuation.

Study participants that started the study are defined as participants that were randomized. Study participants completing the study are those participants completing the SFU Visit, i.e., the participant will be regarded as a completer if the SFU (Day 140) Visit was completed.

Study discontinuation due to AEs will be summarized using the RS. The summary will present the number and percentage of participants who discontinued the study due to an AE by treatment group and overall.

By-participant listings of study participant disposition will be provided by treatment group using the All Study Participants Set, and will include the following:

- Study termination/completion status
- Date of informed consent
- Date of randomization
- Date and time of study medication administration
- Date of last contact
- Date of premature study termination for successfully screened participants dropping out of the study
- Date of screen failure for screen failure participants (based on the later screening visit in case of rescreen)
- Primary reason for premature study termination, as applicable
- Primary reason for screen failure, as applicable (based on the later screening visit in case of rescreen).

By-participant listings of study discontinuation will be presented by treatment group using the RS. The listing will include the primary reason for discontinuation and the number of days since IMP administration.

By-participant listings of visit dates will be presented by treatment group using the SS.

By-participant listings of study participants who did not meet study eligibility criteria will be presented by treatment group using the All Study Participants Set. The listing will include inclusion criteria that were not met and the exclusion criteria that were met. A glossary listing of inclusion and exclusion criteria will also be provided.

By-participant listings of study participant inclusion in each analysis set will be presented by treatment group using the All Study Participants Set.

### **5.3 Efficacy Analyses**

Efficacy is not evaluated in this study.

### **5.4 Pharmacokinetics and Pharmacodynamics Analyses**

#### **5.4.1 Pharmacokinetics**

Unless otherwise specified, all analysis described in this section will be performed on the PKS.

### 5.4.1.1 Descriptive analysis of Pharmacokinetics data

#### Concentration Listings

Individual plasma concentrations of bimekizumab will be listed by treatment group for the SS and will include the actual and nominal PK sampling times, the corresponding time deviations and concentrations. The window allowance document will define the acceptable deviations at each timepoint; samples obtained outside this tolerance will be considered as protocol deviations. All protocol deviations will be discussed at the DEM (Section 5.1.1.4). If a concentration measurement is to be excluded from the analysis of PK parameters, it will be flagged in the listings and the reason for exclusion will be listed/footnoted.

When reporting individual data in listings the following rules will apply:

- Missing data should be reported as no value (NV)
- Concentrations below the lower limit of quantification (LLOQ) will be presented as below the limit of quantification (BLQ) in the listings and the LLOQ value presented as a footnote.
- Concentrations should be listed to the same number of significant figures supplied by the bioanalytical laboratory. Concentrations will be reported in  $\mu\text{g/mL}$ .

#### Concentration Summary Tables

Plasma concentrations of bimekizumab will be summarized by treatment group and nominal sampling time for the PKS. The following descriptive statistics will be presented for plasma concentrations obtained at each nominal time point: n, n(BLQ), arithmetic mean, SD, geometric mean, 95% CI for the geometric mean, geometric CV%, median, minimum, and maximum values.

The geoCV will be calculated using the following formula where SD is the standard deviation of the log-transformed values:

$$\text{Geometric CV (\%)} = \sqrt{(\exp(SD^2) - 1)} \times 100$$

When summarizing the data in tables the following rules will apply:

- To calculate descriptive statistics, all BLQs will be set to half the LLOQ, and the number of BLQs and non-BLQs at each scheduled time point will be reported. Also missing values should be excluded.
- When the total number of BLQ and missing values exceeds one third of the total then only minimum and maximum should be reported for this time point. Other descriptive statistics should be reported as missing ("‐"). The minimum should be reported as BLQ.
- When the mean value includes one or more replaced BLQ values then a footnote should be included to say "contains one or more BLQ value replaced by half the LLOQ value".
- A minimum of 3 values are required to calculate summary statistics. If only 2 values are available, then these should be presented as the minimum and maximum with other descriptive statistics reported as missing ("‐").
- Blood samples for BKZ plasma concentrations collected -/+7 days from the scheduled study assessment will be excluded from the descriptive statistics.

## Concentration Figures

Individual study participant plasma concentration-time profiles of bimekizumab will be displayed graphically on linear and semi-logarithmic scale for the SS. In addition, combined individual (spaghetti) plots will be displayed by treatment group with all study participants in a given treatment group overlaid on the same plot (linear and semi-logarithmic scale) for the SS.

For individual linear/linear and log/linear graphs, actual sampling times should be used and all BLQ values will be substituted as follows:

- BLQs at the beginning of a participant profile (i.e., before the first incidence of a measurable concentration) will be assigned to zero. When using log/linear scale, these timepoints will be considered missing.
- BLQs at the end of a participant profile (i.e., after the last incidence of a measurable concentration) will be set to missing.
- Single BLQs which fall between two measurable concentrations will be set to missing.
- Consecutive BLQs which fall between measurable concentrations will be set to missing.

When summarizing the data in figures the following rules will apply:

- The data plotted in the figure should match the data presented in the summary table (with the exception of missing values prior to  $C_{max}$  which should be set to 0 in the figure to capture lag-time).
- Geometric mean should be plotted (as opposed to arithmetic mean) due to the log-normal distribution of concentrations. Variability should be plotted as detransformed SD computed on ln-transformed data.
- Nominal sampling times should be used.
- Both linear and semi-logarithmic scales should normally be presented.
- All BLQ values will be substituted with  $\frac{1}{2}$  the LLOQ and displayed in the figures.

Geometric mean profiles for each treatment group with lower and upper limits of the 95% CI for the linear scale and the semilogarithmic scale will be displayed for the PKS. The plots on the linear and semilogarithmic scales will be displayed on the same page.

All figures will include a reference line for the LLOQ on the semi-logarithmic panel.

Figures will be generated in black and white using unique line style and marker for each plot in the graph. For all PK concentration-time plots, linear scale will be used for x-axis (e.g., do not use an ordinal scale).

### 5.4.1.2 Pharmacokinetics Parameters

PK parameters will be calculated by Non-Compartmental Analysis (NCA) methods from the concentration-time data using Phoenix® WinNonlin® Version <8.2> or higher following these guidelines:

- Actual time from dose will be used in the calculation of all derived pharmacokinetic parameters.

- There will be no imputation of missing data.
- Handling of BLQ samples for derivation of plasma PK parameters after single dose administration
  - BLQs at the beginning of a participant profile (i.e., before the first incidence of a measurable concentration) will be assigned to zero.
  - BLQs at the end of a participant profile (i.e., after the last incidence of a measurable concentration) will be set to missing.
  - Single BLQs which fall between two measurable concentrations will be set to missing.
  - Consecutive BLQs which fall between measurable concentrations will be set to missing.
- If participants withdrew early from the study the PK scientist's best knowledge will determine which PK parameters from these study participants shall be included in the statistical analysis. The impact of any excluded values will be assessed in the sensitivity analysis.

Pharmacokinetic parameters will be estimated according to the guidelines presented in [Table 5–3](#).

**Table 5–3: Pharmacokinetic Parameter and Estimation**

Parameter	Guideline for Derivation
AUC 0-t	
The AUC from zero time (pre-dose) to the time of last quantifiable concentration will be calculated by a combination of linear and logarithmic trapezoidal methods. Unless specifically requested and justified, the linear up/log down trapezoidal method will be employed.
 
The AUC0-t is the sum of areas up to the time of the last quantifiable sample:
 $AUC_{0-t} = \int_0^t C_{last} * dt$
AUC	
The area from zero time extrapolated to infinite time will be calculated as follows:
 $AUC = AUC_{0-t} + \frac{C_{last}}{\lambda_z}$ 
where Clast is the last observed quantifiable concentration.

%AUC extr	
The percentage of AUC obtained by extrapolation will be calculated as follows:
 $\%AUC_{extr} = \frac{AUC - AUC_{0-t}}{AUC} * 100$ 
Unless otherwise determined by PK Scientist's best knowledge and judgment, if the %AUCextr is greater than 20% the value, %AUCextr, and all dependent parameters (ie, AUC, MRT, Vz and CL) will be flagged in summary tables and will still be included in the calculation of summary statistics. The reason for flagging will be listed/footnoted in parameter summary tables.

C max	
Maximum concentration, obtained directly from the observed concentration versus time curve. In the case of bioequivalence studies, the FDA guidance should be followed: if the predose concentration is <math>\leq</math> 5 percent of the Cmax value in that study participant, the study participant's data without any adjustments can be included in all pharmacokinetic measurements and calculations. It is recommended that if the predose value is <math>></math> 5 percent of Cmax, the study participant be dropped from all bioequivalence study evaluations.

Parameter	Guideline for Derivation
CL/F	Apparent systemic clearance of parent drug will be calculated from: $CL/F = \frac{Dose}{AUC}$
$\lambda_z$	First order terminal elimination constant or apparent first order terminal elimination rate constant, for compound representing release/absorption as limiting steps 1. The apparent terminal phase rate-constant ( $\lambda_z$ ) will be estimated by linear regression of concentration versus time data presented in a log-linear scale. 2. Data are primarily monotonically decreasing in magnitude and are representative of the actual decline in the log concentration-time curve. 3. Only those data points that are judged to describe the terminal log-linear decline will be used in the regression. 4. A minimum number of three data points in the terminal phase will be used in calculating $\lambda_z$ with the line of regression starting at any post- $C_{max}$ data point ( $C_{max}$ should not be part of the regression slope). Unless otherwise determined by PK Scientist's best knowledge and judgment or if instructed by the Sponsor, if the adjusted correlation coefficient (R2 adjusted) is <0.8, then $\lambda_z$ and all the $\lambda_z$ dependent parameters (i.e. $t_{1/2}$ , AUC, CL, MRT, and $V_z$ ) will be flagged in summary tables of PK parameters and will still be included in the calculation of the summary statistics. The reason for flagging will be listed/footnoted in parameter summary tables. 5. Unless otherwise determined by PK Scientist's best knowledge and judgment, the interval used to determine $\lambda_z$ should be equal or greater than 2-fold the estimated $t_{1/2}$ , and if less than 2-fold, $\lambda_z$ will be flagged in summary tables and statistical analysis of PK parameters and will still be included in the calculation of the summary statistics. All the derived parameters (i.e. $t_{1/2}$ , AUC, CL, MRT, and $V_z$ ) may also be flagged in summary tables of PK parameters. The reason for flagging will be listed/footnoted in parameter summary tables. 7. Best practice is to let Phoenix determine the terminal $\lambda_z$ automatically. Each determination must then be checked manually. Data points may be dropped from the linear regression if the PK Scientist considers the reported values to be anomalous. Any data points so designated should remain in the PK concentration listings with a footnote and be identified in the study report with a rationale for exclusion.
$t_{max}$	Time of $C_{max}$ , obtained directly from the observed concentration versus time curve [if two identical values are recorded for $C_{max}$ , the first one will be considered $t_{max}$ ]
$t_{1/2}$	The terminal elimination half-life will be calculated as follows: $t_{1/2} = \frac{\ln 2}{\lambda_z} = \frac{0.693}{\lambda_z}$
$V_z/F$	Apparent volume of distribution $V_z = \frac{CL/F}{\lambda_z}$

 FDA Guidance for Industry: Bioavailability and Bioequivalence – Studies for Orally Administered Drug Products – General Considerations (2003)

## PK Parameter Summaries

PK parameters will be listed in summary tables by participant for the PKS.

When reporting individual data in summary tables the following rules will apply:

- Individual PK parameters should be reported to 3 significant figures.
- If a parameter cannot be calculated it should be reported as NE (not estimable ie, if input data is missing which prevents calculation).

- Based on the rules in [Table 5-3](#), individual PK parameters in the summary tables that are flagged as unreliable will be footnoted with the reason and will be included in the calculation of the summary statistics.

Biostatistics group will consider the derived PK parameters as source data and will use this data without rounding for calculation of PK parameters summary statistics tables.

PK parameters will be summarized by treatment group for the PKS.

When summarizing the data in tables the following rules will apply:

- Tabular summaries for PK parameters will report N (number of study participants per treatment group) and n (number of study participants with non-missing values).
- For most PK parameters (ie, for continuous variables) the following descriptive statistics should be calculated: arithmetic mean, median, SD, minimum, maximum, geometric mean, geoCV and 95% CI for the geometric mean. For  $t_{max}$  (ie, for discontinuous variables) only median, minimum and maximum should be reported.
- Descriptive statistics should be reported to 4 significant figures for mean, median and SD and to 3 significant figures for all others.
- If at least two thirds of the study participants have a PK parameter reported then descriptive statistics will be calculated, otherwise only minimum and maximum will be reported for this PK parameter and all other descriptive statistics will be reported as NE (ie, not estimable).
- A minimum of 3 values are required to calculate summary statistics. If only 2 values are available, then these should be presented as the minimum and maximum with other descriptive statistics reported as missing ("‐").

## PK Parameter Figures

Box plots of primary PK parameters (AUC,  $AUC_{0-t}$  and  $C_{max}$ ) will be generated comparing two treatment groups.

### 5.4.2 Statistical analysis of bioequivalence

#### 5.4.2.1 Primary analysis

Following  $\log_e$ -transformation, the primary PK parameters (AUC,  $AUC_{(0-t)}$  and  $C_{max}$ ) will each be evaluated according to an analysis of variance (ANOVA) model with a fixed effect term for pair and treatment.

For comparison of bimekizumab-AI-2mL (test) versus bimekizumab-AI-2x1mL (reference) treatment, the difference between the least squares means (LSMs) will be estimated and back transformed in order to obtain the GMR and associated 90% CI for the ratio. Bioequivalence will be concluded if the 90% CIs for the ratio of the comparison is fully included in the acceptance range from 0.8 (80%) to 1.25 (125%) for AUC,  $AUC_{(0-t)}$ , and  $C_{max}$ .

All study participants in the PKS will be included in the analysis as far as the data permit; a study participant may be included in the analysis for one or more PK parameters (i.e., if it was not possible to calculate AUC for a given participant, the participant may be included in the analysis of BE for  $AUC_{(0-t)}$  and  $C_{max}$ ).

The results of the BE analysis will be tabulated, including the geometric LSMS and 95% CI for treatment group, the estimated GMR and 90% CI, and CV% for the bimekizumab-AI-2mL (test) versus bimekizumab-AI-2x1mL (reference) treatment.

#### 5.4.2.2 Secondary analysis

A similar ANOVA, as described in Section 5.4.2.1, will be performed on  $\log_e$ -transformed  $t_{1/2}$  to compare elimination characteristics between treatment groups.

The point estimate and the 90% CI for the median treatment differences for  $t_{max}$  will be computed according to the Hodges-Lehmann's method.

#### 5.4.2.3 Sensitivity analysis

The following sensitivity analyses will be performed following the same model as described for the primary analysis (Section 5.4.2.1):

1. Including main effect of site
2. Including both main effect of site and site-by-treatment interaction
3. Based on all nonpositive ADAb study participants (defined as any positive ADAb observed post-Baseline)
4. Including body weight at Day -1 as covariate
5. Corrected for measured protein content:

For compliance with Canadian Health ministry guidance, AUC and  $C_{max}$  ratio estimates and 90% CIs will be also presented as corrected for measured protein content (potency). A correction factor (CF) will be obtained as the ln-transformed ratio of the percent protein content (Reference/Test). Then, this factor will be added to the difference in LSMS to obtain, by exponentiation, the corrected AUC and  $C_{max}$  geometric mean ratios and the corresponding 90% CIs.

For a given Reference/Test, the correction factor will be calculated using the below formula:

$$CF = \ln\left(\frac{\% \text{ Measured Content Reference}}{\% \text{ Measured Content Test}}\right) \quad [3]$$

The corrected ratio estimate for the PK parameter (AUC or  $C_{max}$ ) is calculated using the below formula:

$$\text{Ratio} = 100 \times \exp(LSM \text{ difference} + CF) \quad [4]$$

Where,

$$LSM \text{ difference} = LSM(\text{Test}) - LSM(\text{Reference}) \quad [5]$$

The corrected 90% CI for the ratio is obtained using the below formula:

$$90\% \text{ CI} = 100 \times \exp[(LSM \text{ difference} + CF) \pm t_{0.05,df} \times se(LSM \text{ difference})] \quad [6]$$

6. Including all excluded and available PK parameters

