**Table 1-1: Schedule of study assessments overview**

Assessments	Screening	Inhouse Treatment Period			Outpatient Visits			Early Withdrawal a / SafetyFollow-Up/ Visits
		Day -1	Day 1		Day 1 postdose to Day 3 postdose	Days 4 to 10	Days 13, 16, 19, 22, 25, and 28 (±1 days)	
Day -28 to Day -2	Admission	Pre-dose	0 h					Day 140 (±3 day)

- a ADAb samples will be taken predose and on Days 13, 28, 56, 84, 112, and 140; blood samples will be processed as specified in the laboratory manual. If feasible, an additional blood sample for PK and ADAb analysis should be collected from participants who develop a hypersensitivity reaction. The sample should be obtained close to the time of the event using an unscheduled visit if needed.
- P Pregnancy tests will be performed at the Screening Visit, Day-1, Days 28, 56, 84, 112, and Day 140. Prior to dosing (at Screening and Day -1), the test should be performed in serum; post dosing the test may be performed in urine. The FSH test will be performed in postmenopausal women at the Screening Visit. Additional details are provided in Appendix 4 (Section 10.4).

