## **9.4 Planned outcome analyses**

### **9.4.1 Primary endpoint analyses**

The PK analyses will be performed on the PKS.

Following  $\log_e$ -transformation, the primary PK parameters ( $C_{\max}$ , area under the plasma concentration-time curve from time zero to the last quantifiable concentration [ $AUC_{(0-t)}$ ], and AUC) will each be evaluated according to an analysis of variance (ANOVA) model with a fixed effect term for pair and treatment. The estimate of the ratio of geometric mean for the AI-2mL (test) versus 2xbimekizumab-AI-1mL (reference) treatment along with the associated 90% confidence intervals (CIs) for the ratio will be calculated. Bioequivalence will be concluded if the 90% CIs for the ratio of the comparison is fully included in the acceptance range from 0.8 to 1.25 for AUC,  $AUC_{(0-t)}$ , and  $C_{\max}$ .

Two sensitivity analyses will add 1) the main effect of center and 2) both main effect of center and center-by-treatment interaction. Further sensitivity analyses may also be performed on the PK parameters.

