#### Study participant Classification:

- A study participant will be classified as having ADAb positivity at Baseline if the Day 1, Predose result is ADAb+;
- A study participant will be classified as overall positive if at least one post-Baseline measurement is ADAb+;
- A study participant will be classified as overall negative if at all post-Baseline visits the ADAb status is negative (this includes study participants who have ADAb+ results at Baseline) or only one sample is missing and all other ADAb samples are negative;
- Missing if the study participant has missed more than one ADAb sample and all other available ADAb samples are negative;
- A participant will be classified as having treatment-emergent ADAb positivity when meeting one of the following criteria:
  - The Baseline result is ADAb-, and at least one post-Baseline time point is ADAb+;
  - The Baseline result is ADAb+, and at least one post-Baseline measurement shows a 1.81-fold increase in titer from the Baseline value (the Minimum Significant Ratio [MSR] in healthy study participants).

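### SAP 5.4.2.3 item 3 labels its subset nonpositive for ADAb but defines it by the condition for overall positive, so read literally it selects the opposite group (one sensitivity analysis only)

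*SAP*

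**What the plan says.** SAP 5.4.2.3 lists six sensitivity analyses that follow the primary model of SAP 5.4.2.1. Item 3 reads "Based on all nonpositive ADAb study participants (defined as any positive ADAb observed post-Baseline".

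SAP 5.5.1, under Study participant Classification, sorts participants by their post-Baseline results into three classes:

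- Overall positive: "A study participant will be classified as overall positive if at least one post-Baseline measurement is" ADAb+.
- Overall negative: "A study participant will be classified as overall negative if at all post-Baseline visits the" status is negative, "or only one sample is missing and all other" samples are negative. A positive result at Baseline does not prevent this.
- Missing: "Missing if the study participant has missed more than one" sample and all available ones are negative.

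The term nonpositive is not defined anywhere else in the SAP. The protocol does not help. Section 9.4.1 says "Two sensitivity analyses will add 1) the main effect of center and 2) both main effect of center and center-by-treatment interaction" and then only that "Further sensitivity analyses may also be performed on the PK parameters". Item 3 is therefore the sole specification of this subset.

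The SAP version history shows that version 2.0 added an analysis to 5.4.2.3. It lists no correction to item 3, so the wording is current.

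**The concern.** The label and the definition in item 3 contradict each other. A programmer who implements the definition would analyse only participants with a positive post-Baseline result. One who implements the label would analyse everyone else. These two groups have no member in common, so the choice decides the whole content of the analysis.

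The analysis presumably exists to show whether the bioequivalence result holds once participants who developed antibodies are set aside. The literal rule cannot show that. Running the sensible version means departing from the stated definition, and the SAP records no basis for doing so.

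**Working it through.** The plan attaches no figure to this subset, so there is none to reproduce. The check has two parts.

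**1. Logic of the definition**

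Input: the Schedule of activities (protocol Table 1-1 notes) states "ADAb samples will be taken predose and on Days 13, 28, 56, 84, 112, and 140", which gives six post-Baseline samples. Each can be positive, negative or missing.

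- All result patterns: 3^6 = 729.
- Patterns with no positive: 2^6 = 64.
- Patterns with at least one positive: 729 − 64 = 665.
- Among the 64, no sample or one sample missing: 1 + 6 = 7, overall negative under 5.5.1.
- Among the 64, more than one missing: 64 − 7 = 57, Missing under 5.5.1.

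| Class in SAP 5.5.1 | Patterns | Kept by item 3 as written | Kept if overall positive is excluded |
|---|---|---|---|
| Overall positive | 665 | 665 | 0 |
| Overall negative | 7 | 0 | 7 |
| Missing | 57 | 0 | 57 |

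The written condition is identical to overall positive and shares nothing with the labelled group. These are counts of patterns, not expected numbers of participants.

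**2. What each reading leaves for the model**

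Item 3 uses the primary model, an ANOVA on the log scale with fixed effects for pair and treatment (SAP 5.4.2.1). A participant whose partner is removed is absorbed by the pair term. Only pairs with both members in the subset inform the treatment contrast, so intact pairs are the relevant count, not headcount.

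Inputs:

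- Pairs: 60, from 60 participants per group (SAP 3) matched one to one (SAP 1.2). Taking all 60 as complete is an assumption and a favourable one.
- Positive rate p: not in the documents. Assumed 10%, 20% and 30%.
- ADAb status independent within pairs: an assumption.

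Formulas for the expected number of intact pairs:

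- Literal rule, both members positive: 60 × p².
- Intended rule, neither member positive: 60 × (1 − p)².

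| p | Literal rule | Intended rule |
|---|---|---|
| 10% | 60 × 0.01 = 0.6 | 60 × 0.81 = 48.6 |
| 20% | 60 × 0.04 = 2.4 | 60 × 0.64 = 38.4 |
| 30% | 60 × 0.09 = 5.4 | 60 × 0.49 = 29.4 |

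With k intact pairs the model has 2k − k − 1 = k − 1 residual degrees of freedom, so at least two are needed for a confidence interval. At p = 10% the literal rule would usually give none. If only 54 pairs were complete (54 per group is the number required in SAP 3), every entry shrinks by 54/60 = 0.9.

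**The case against.** The strongest reply is that this is a drafting slip with a plain meaning. The parenthesis repeats the 5.5.1 condition for overall positive almost exactly, so it can be read as saying what positive means, with the prefix in the label negating it. An analyst is unlikely to run a positives-only analysis under the name nonpositive, and at low ADAb rates such an analysis would fail visibly. This largely stands: the intent is recoverable, and that limits how serious the point is. It does not make the definition correct. The sentence presents the condition as defining the nonpositive group, and nothing else in either document says otherwise.

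A reader might also infer that the treatment of the Missing class is a sizeable open question. The documents do not support that. Item 3 does not use the defined term overall negative. Nonpositive in its ordinary sense covers everyone who is not overall positive, which already points to keeping the Missing class. Its size cannot be estimated either. Participants who withdraw have an Early Withdrawal visit with the same assessments as the Safety Follow-Up Visit, including an ADAb sample (Table 1-1 and its notes; see also protocol 8.10). The plan does not say how that sample counts towards the number missed.

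Finally, the pair counts rest on assumed ADAb rates. That is true. They show the contrast between the two readings and predict nothing about this trial.

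**Conclusion.** The definition in item 3 is wrong as written: it selects exactly the participants that its label excludes. This follows from SAP 5.4.2.3 and 5.5.1 alone and needs no assumption about rates. The pair counts do depend on assumptions (60 complete pairs, independence within pairs, positive rates of 10% to 30%). On those, the literal rule leaves between one and six intact pairs at most in expectation, and the intended rule roughly 29 to 49.

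The point is minor and should be corrected. A reader might infer that the bioequivalence conclusion is at risk, or that the sponsor means to analyse antibody-positive participants. Neither inference is supported. The primary analysis includes all PKS participants as far as the data permit, without restriction by ADAb status, and its decision rule does not refer to item 3. The label points to exclusion of the positives.

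**What to change.** Replace item 3 of SAP 5.4.2.3 with:

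> Excluding participants classified as overall ADAb positive per Section 5.5.1 (at least one ADAb+ post-Baseline result).

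Under this wording participants classed as Missing stay in, which agrees with nonpositive and needs no further rule.

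The cost is one sentence. It calls for no new data, no additional analysis and no change to the primary model or decision rule. SAP Section 1 requires an SAP amendment when analysis definitions are modified before database lock, so the correction belongs in one. If lock has already passed, the reading that was applied and the reason for it should be stated in the clinical study report.
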